This study requires 8 visits to the clinic: a screening visit (week -1), a baseline visits (weeks 0, 1 and 2) and then follow up at 2, 4 and 12 weeks after starting the drug. Each visit will consist of blood draw. Subjects will be required to bring in a 24 hour urine sample on weeks 0, 4 and 12.

After the screening visit, subjects will be randomized into 2 groups. The first group will be started on 5 mg linagliptin (supplied by Boehringer Ingelheim Pharmaceuticals, Inc. (BIPI)) daily for 12 weeks. Fructosamine testing will be done at baseline, 4 and 12 weeks (and HbA1c at 0 and 12 weeks) to assess glycemic control. The second group will serve as a control group and will be placed on a placebo (mainly mannitol and corn starch, provided by BIPI in similar shape and color as the active drug) for 12 weeks. Blood samples will be obtained as described for patients on linagliptin. Each blood draw will consist of 45 ml of which 35 ml is collected in EDTA tubes and 10 ml in no-additive tubes. A single dose effect will be investigated at the first day of drug or placebo in 24 subjects (12 from each group) only and blood will be collected at 2, 4 and 6 hr following the first dose. The effect of a standard high-fat high-carbohydrate meal (HFHC) will be investigated on those 12 subjects from each group at baseline and at 12 weeks.

[figure not shown]

Figure 1: Study Design.

STUDY PROCEDURES BY VISIT:

Screening Day

Each subject will complete the following procedures and meet the inclusion and exclusion criteria prior to participating in the study.

1. Medical History
2. Physical Exam
3. Informed consent
4. Baseline lab draws to measure CBC, SMA, lipid profile, fructosamine and HbA1C

Visit 1: Week -2 to Week 0

Visit 1A: The participants will undergo HE clamp. They will be advised to bring 24 hour urine at this visit and research blood will be collected. All patients will have visit A. Visits B and C will be done only in 24 patients (12 in drug group and 12 in placebo group).

Visit 1B: The effect of a standard high-fat high- carbohydrate meal (HFHC) will be investigated in 24 subjects. Fat biopsy will be done before and after the meal.

Visit 1C (in 24 subjects): A single dose (5 mg or placebo) effect will be studied in 24 subjects with blood collections at 2, 4 and 6 hr following the first dose.

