This is a prospective study to evaluate oxidative stress before and after treatment with linagliptin. The similarities between the study groups, baseline values for subject's demographics will be compared using appropriate parametric tests. Transformations of the data on order to meet statistical assumptions may be considered. All statistical analysis will be carried out using SPSS software (SPSS Inc, Chicago, Illinois). Comparison of each endpoint will be made using an analysis of covariance model, with baseline medications, change in BMI and change in HbA1c as covariates. The primary endpoint of the study is to detect a change in JNK-1 protein in MNC before and after linagliptin use as compared to placebo. We have chosen this as the primary endpoint because JNK-1 is an inflammatory mediator that also interferes with insulin signaling. Our prior data with sitagliptin show a 24% fall (with SD of 24%) in JNK-1 following 12 weeks of treatment in type 2 diabetics(55). There was a 6% non-significant increase in JNK-1 protein in the placebo group in that study. Conservatively estimating a difference in change in JNK-1 cellular concentrations of 24% among the two groups, a sample size of 20 patients per group (assuming a drop-out rate of 15%) should provide adequate power ($\beta = 0.2$) to detect a significant difference ($\alpha = 0.05$), provided the standard deviation of the residuals is not equal to or greater than the mean difference (see table below).

Sample Size Estimate

Difference in the mean % change from baseline	Sample Size Estimate			
	5%	10%	15%	20%
10%	5	17	36	62
15%	3	8	17	28
20%	3	5	10	17

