Justification of drop-out rate: The analysis will adjust for only one baseline covariate: baseline medications. Two other covariates are change in BMI (which is not expected with linagliptin or placebo) and change in HbA1c. Sulfonylureas, metformin and subcutaneous insulin are not likely to induce insulin sensitization or decrease inflammation. Subjects currently on GLP-1 agonists or DPP-IV inhibitors will be excluded from the study. Thiazolidinediones can induce insulin sensitization as well as decrease inflammation. The use of thiazolidinediones should be equally distributed among the two groups. Less than 20% of our research subjects are on thiazolidinediones. Therefore it is likely that adjustment for thiazolidinediones should decrease sample size by <5%. Based on this justification and on our previous experience in diabetes trials, we have estimated that our drop-out rate will be 15% of 20 patients (3 patients per group).

The secondary endpoints for the study will be comparison of the relative change from baseline in a) inflammatory mediators in serum and adipose tissue, b) single dose effect of linagliptin on inflammation and oxidative stress, c) HFHC induced inflammation in serum and adipose tissue and d) insulin sensitivity and hepatic glucose output; before and after using Linagliptin for 12 weeks.

FACILITIES

LABORATORY: The Diabetes-Endocrinology Center of Western New York Research Laboratories at SUNY at Buffalo, contain 6 laboratories with space totaling approximately 1600 Qs ft designated for research purposes. These labs are dedicated for the P.I. research. There is a cold room, dark room and four labs have fume hoods. In addition, six offices (600 Qs ft) are attached to the labs for lab staff.

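### Read as written, the plan's single ANCOVA adjusts the 2 to 6 hour single-dose response for an HbA1c change that is not known until week 12

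*Combined protocol and SAP*

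**What the plan says.** The Data Analysis section gives a single model and applies it to all endpoints: "Comparison of each endpoint will be made using an analysis of covariance model, with baseline medications, change in BMI and change in HbA1c as covariates". In the paragraph headed Justification of drop-out rate, the plan confirms that only one of these covariates precedes treatment ("The analysis will adjust for only one baseline covariate: baseline medications") and names the others as "change in BMI (which is not expected with linagliptin or placebo) and change in HbA1c". The interval over which either change is taken is not stated.

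The secondary endpoints follow in the same section. Item (b) is the "single dose effect of linagliptin on inflammation and oxidative stress". The list closes with "before and after using Linagliptin for 12 weeks", which fits the 12-week items but not this one. No other model is given for Hypothesis 2 or Aim 2.1.

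On timing, Visit 1C says the single-dose "effect will be studied in 24 subjects with blood collections at 2, 4 and 6 hr following the first dose"; Study Design gives the split as 12 per group. For HbA1c, Study Design says "Fructosamine testing will be done at baseline, 4 and 12 weeks (and HbA1c at 0 and 12 weeks) to assess glycemic control", and the Screening Day list adds "Baseline lab draws to measure CBC, SMA, lipid profile, fructosamine and HbA1C". For patients who attend Visit 1C, the protocol counts the start of that visit as week 0. The Rationale for study says that linagliptin improves glycaemic control.

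**The concern.** A covariate that is fixed before treatment can sharpen a randomised comparison without changing what it estimates. A covariate measured after treatment, and affected by it, can change what is estimated. Here the order of events also rules out the usual defence. For a 12-week endpoint one might argue that HbA1c change is a mediator whose contribution should be separated out. For a response that is over by hour 6, an HbA1c change completed about 12 weeks later can be neither a mediator nor a confounder.

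The Hypothesis 2 estimate is at stake. If patients with a larger acute fall in an inflammatory marker later have a larger HbA1c fall, the adjustment removes part of a genuine acute effect. If the association runs the other way, it inflates the effect. With no acute effect at all, it can create an apparent one. The protocol's own reasoning makes an association conceivable, since it proposes that suppressing inflammatory mediators may improve insulin sensitivity.

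There is also a practical consequence. The plan gives no missing-data method. Under a complete-case analysis, a patient without a week-12 HbA1c drops out of the single-dose comparison although the 6-hour data are complete.

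**Working it through.** **The plan's own figure.** For the primary endpoint the plan takes a difference of 24 points, α = 0.05, power 0.80 and 15% drop-out. With SD 24, a two-sided two-sample comparison needs 16 per group by the normal formula and 17 by the t distribution, and 17 / 0.85 = 20. The stated 20 per group is reproduced (power 0.807 with 17). No sample size or power is stated for the single-dose endpoint.

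**Timing, which needs no assumption.**
- Response: 2, 4 and 6 hours after the first dose, at week 0.
- HbA1c: screening, week 0 and week 12. Week 4 has fructosamine only.
- An on-treatment HbA1c change therefore exists only about 12 weeks after the response. A screening-to-week-0 change could be computed, but it is not a change on treatment and nothing in the plan points to it.

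**Size, which is illustrative.** Inputs:
- 12 per arm (Study Design).
- SD 24% and a true difference of -24 points, borrowed from the 12-week JNK-1 planning values. The documents give no acute values.
- d, the reduction in HbA1c change due to treatment, in SD units: assumed 0.25, 0.5 or 1.
- r, the within-arm correlation, positive when a larger HbA1c fall goes with a larger marker fall: assumed 0, +0.3 or -0.3, first taken as equal in both arms.
- HbA1c change is the only covariate in the illustration. BMI change is left out because its measurement times are not given and the plan expects none.

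Formulas:
- Unadjusted SE = 24 × √(2/12) = 9.80.
- Shift in the estimate = r × 24 × d. For r = 0.3 this is 0.3 × 24 × 0.25 = 1.8, then 3.6 and 7.2; the sign follows r.
- Adjusted SE (large-sample) = 9.80 × √(1 - r²) × √(1 + d²/4).

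| | d = 0.25 | d = 0.5 | d = 1 |
|---|---|---|---|
| SE, r = 0 | 9.87 | 10.10 | 10.95 |
| SE, r = ±0.3 | 9.42 | 9.63 | 10.45 |
| Mean estimate, r = +0.3 (true -24) | -22.3 | -20.4 | -16.8 |
| Power, r = +0.3 | 60% | 50% | 33% |
| Mean estimate, r = -0.3 (true -24) | -25.8 | -27.6 | -31.2 |
| Power, r = -0.3 | 72% | 76% | 78% |
| Power, r = 0 (no bias) | 63% | 60% | 54% |
| Rejection with no true effect, r = ±0.3 | about 5% | about 6% | about 10% |

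Mean estimates, power and rejection rates come from simulation, 20,000 runs per cell. Without the covariate the mean estimate is -24 and power is 65%.

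**Unequal correlation.** If acute and later response are linked only in patients on drug, take r = 0.3 in the active arm and 0 on placebo. With equal arms the pooled slope uses the average, 0.15, so the shift is 0.15 × 24 × d = 0.9, 1.8 and 3.6 points, half of the above. Simulated rejection with no true effect is then about 5.2%, 5.4% and 6.5%.

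**The case against.** The strongest reply is that the premise is inferred. The plan gives no interval for the HbA1c change and nowhere says that a week 0 to 12 change enters a model for a same-day response. A change covariate could mean change over the endpoint's own interval; none is measured within a day, so the term would drop out. The words that close the endpoint list suggest that the model was written with 12-week endpoints in mind. This is a fair account of what the authors may have intended. It is not what the text says: the model rule covers every endpoint, the single-dose effect is on the list, and no exemption or alternative model appears.

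The second reply is that the size rests on values from outside the documents. That stands. Neither d nor r is given, the SD and difference are 12-week values, and the largest figures need a shift of a full SD. The entry limit of HbA1c 7.5% or below may keep d small, and at d = 0.25 the false-positive rate is essentially nominal. Equal correlation in both arms is a further assumption, and relaxing it halves the shift.

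Third, a covariate need not be a cause to reduce residual variance. This is also correct: with r = ±0.3 the SE falls below 9.80 for the two smaller shifts. A reader might infer that the covariate brings no benefit of any kind, but the figures do not support that. The objection is that any precision gained this way surrounds a shifted estimate.

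**Conclusion.** The concern holds for the plan as written. The model rule, applied literally, adjusts the acute response for a post-randomisation variable measured about 12 weeks later. The timing mismatch rests on the documents alone. The harm does not: it runs from zero bias with some loss of precision (r = 0) to a shift of 7.2 points and a false-positive rate of about 10% (|r| = 0.3 in both arms, d = 1 SD). These figures are illustrations, not predictions.

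Three stronger conclusions might be inferred, and the documents support none of them:
- That the acute effect will be underestimated. The direction depends on the sign of a correlation that the documents do not give, and it may be zero.
- That the authors have decided to use the week-12 change for this endpoint. The interval is unstated and the closing words of the endpoint list point the other way.
- That the main result is compromised by this mismatch. The primary endpoint is a 12-week change, and its sample size of 20 per group is unaffected.

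The point should still be settled before analysis. It concerns one of four named hypotheses, tested in 12 patients per arm with about 65% power under the borrowed values, and an unstated exemption would leave the choice of model until after the data are seen.

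**What to change.** Add one sentence to the Data Analysis section: the single-dose endpoint is analysed without the change-in-BMI and change-in-HbA1c covariates, using treatment and pre-dose covariates only. Baseline medications already qualify. The marker's own pre-dose value may be added at the cost of one degree of freedom; whether it improves precision depends on a correlation that the documents do not give.

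The cost is that one sentence. It needs no new data, visits or patients, and it keeps in the comparison any patient who has complete 6-hour data but no week-12 HbA1c.

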Linagliptin has been shown to result in better glycemic control in type II diabetes patients. As described above, obesity and diabetes are states of increased inflammation and are also major risk factors for atherosclerotic disease. In view of the data suggesting that DPP-IV is a pro-inflammatory mediator and that its inhibition may suppress autoimmune inflammatory mechanisms, it is likely that linagliptin may exert an anti-inflammatory effect in the human. The increase in GLP-1 concentrations may also exert an anti-inflammatory effect similar to that observed with exenatide. Indeed, our investigations on the anti-inflammatory effects of sitagliptin, the first DPP-IV inhibitor to be licensed, have demonstrated profound evidence to this effect. Our findings are summarized under preliminary data below.

Preliminary data:

In a study on obese type 2 diabetics, the administration of sitagliptin 100 mg daily for 12 weeks resulted in several novel observations. There was an inhibition of DPP-IV enzyme by 90% within 2 hours of the first dose. In addition, there was a suppression of CD26 expression. CD26 is a pro-inflammatory mediator expressed on the cell membranes and is the cellular analog of the DPP-IV enzyme. Thus, sitagliptin and possibly other DPP-IV inhibitors may also inhibit the expression and synthesis of DPP-IV. In addition, there was a reduction in plasma concentrations of FFA, CRP and IL-6; a reduction in the expression of CCR-2, IKK β , JNK-1, TNF α (see figures below).

[figure not shown]
[figure not shown]
[figure not shown]
[figure not shown]
[figure not shown]

Figure 1: Change in DPP-IV activity (A), GLP-1 Concentrations (B) and CD26 mRNA in MNC (C) following placebo and Sitagliptin 100mg daily for 12 weeks in type 2 diabetic subjects. N=12 each, data are presented as mean \pm SE. (*, **: $P<0.05$ by RMANOVA (compared to baseline) in sitagliptin and placebo groups, respectively, #: $P<0.05$ by Two-way RMANOVA compared to control groups.

[figure not shown]
[figure not shown]
[figure not shown]

Figure 2: Percent Change in mRNA expression of JNK-1(A), TNF- α , (B) TLR-4 (C), CCR-2 (D) and IKK- β (E) in MNC following placebo and Sitagliptin 100mg daily for 12 weeks in type 2 diabetic subjects. N=12 each, data are presented as mean \pm SE. (*, **: $P<0.05$ by RMANOVA (compared to baseline) in sitagliptin and placebo groups, respectively, #: $P<0.05$ by Two-way RMANOVA compared to control groups.)

[figure not shown]

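### The only stated model for every endpoint, including primary JNK-1, adjusts for changes in HbA1c and BMI that arise after randomisation, so it does not target the total linagliptin-versus-placebo effect the trial is sized on

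*Combined protocol and SAP*

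**What the plan says.** The Data Analysis section names a single model, stating that the comparison for "each endpoint will be made using an analysis of covariance model, with baseline medications, change in BMI and change in HbA1c as covariates". A later paragraph, justifying the drop-out rate, confirms how the covariates are classed: "The analysis will adjust for only one baseline covariate: baseline medications". It continues: "Two other covariates are change in BMI (which is not expected with linagliptin or placebo) and change in HbA1c".

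The primary endpoint is to "detect a change in JNK-1 protein in MNC before and after linagliptin use as compared to placebo". The sizing rests on an overall 12-week result: "Our prior data with sitagliptin show a 24% fall (with SD of 24%) in JNK-1 following 12 weeks of treatment". From this the plan takes a between-group difference of 24 points, 20 patients per group and 15% drop-out, "provided the standard deviation of the residuals is not equal to or greater than the mean difference".

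On HbA1c, the Rationale for study states: "Linagliptin has been shown to result in better glycemic control in type II diabetes patients". Study Design schedules "HbA1c at 0 and 12 weeks) to assess glycemic control".

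No analysis without the two change covariates is described. The parametric tests mentioned in Data Analysis are for baseline demographics, and the repeated-measures analyses in the figure captions belong to the earlier sitagliptin study. None of the four hypotheses or their aims asks for an effect independent of glycaemia.

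**The concern.** Randomisation makes the arms comparable on everything fixed beforehand. It does not make them comparable among patients with the same later change in HbA1c. If linagliptin lowers HbA1c, the fitted treatment coefficient compares a linagliptin patient with a placebo patient who reached the same HbA1c change for other reasons. That coefficient equals the total effect only if HbA1c change is unrelated to JNK-1 change within arms, or if linagliptin does not shift HbA1c in this trial. The plan establishes neither.

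A link is plausible on the protocol's own account. The background says glucose intake induces oxidative stress and raises NFκB. JNK-1 was chosen because it interferes with insulin signalling, so a fall in JNK-1 might also feed through to HbA1c. No correlation between the two changes is reported.

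This is the only stated primary test, so a reader could not tell how far the reported JNK-1 difference departs from the randomised comparison. The rule also covers secondary endpoints. Insulin sensitivity and hepatic glucose output would be adjusted for glycaemic change. Read literally, the single-dose response at 2 to 6 hours would be adjusted for changes that arise after it is measured; the plan does not define the window of change for that endpoint.

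**Working it through.** **1. Reproducing the sample size.** Inputs from Data Analysis: difference 24, SD 24 (the sitagliptin SD; its use here is inferred), α 0.05 (taken as two-sided), power 0.80. A two-sample t-test needs 16.7, so 17 per group, and 17/0.85 = 20. Power at 17 per group is 0.807. The plan's table also gives 17 wherever the difference equals what appears to be the SD. The stated size is therefore that of a plain comparison of mean changes, which is the total effect.

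**2. What the written model estimates.** Let Δ be the total effect on JNK-1 change, σ its within-arm SD, d the fall in HbA1c due to treatment, s the within-arm SD of HbA1c change, and ρ the within-arm correlation of the two changes. The within-arm slope is σρ/s, and the arms differ in mean HbA1c change by -d, so

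expected adjusted estimate = Δ + σρd/s.

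Example: Δ = -24, σ = 24, ρ = 0.5, d = 0.3, s = 0.5 gives -24 + 24 × 0.5 × 0.6 = -16.8.

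Because treatment predicts HbA1c change, the variance of the coefficient is also inflated by 1 + (d/2s)². For d = 0.1, 0.3 and 0.5 this is 1.01, 1.09 and 1.25.

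**3. Illustration.** From the documents: 17 per arm (20 less 3) and Δ = -24. Inferred: σ = 24. Assumed, not in the documents: d, s = 0.5%, ρ, and 20% of patients in a binary medication covariate. BMI change is simulated as noise. There were 40,000 simulated trials per setting. Each cell shows the expected estimate, then power.

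| HbA1c shift | ρ = -0.3 | ρ = 0 | ρ = 0.2 | ρ = 0.3 | ρ = 0.5 |
|---|---|---|---|---|---|
| 0.1% | -25.4; 0.840 | -24.0; 0.756 | -23.0; 0.743 | -22.6; 0.752 | -21.6; 0.790 |
| 0.3% | -28.3; 0.882 | -24.0; 0.730 | -21.1; 0.640 | -19.7; 0.596 | -16.8; 0.545 |
| 0.5% | -31.2; 0.899 | -24.0; 0.672 | -19.2; 0.501 | -16.8; 0.421 | -12.0; 0.285 |

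For comparison, power is 0.807 with no covariates, 0.793 with medications only, and 0.763 with three covariates unrelated to treatment. The step from 0.793 to 0.763 is the price of two extra terms with 34 patients and is not bias.

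**4. With no true effect** (nominal 0.025 in each direction), for shifts of 0.1, 0.3 and 0.5%:

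- ρ = -0.3: rejections favouring linagliptin are 0.037, 0.071 and 0.116.
- ρ = 0: about 0.025 each way throughout.
- ρ = 0.5: rejections for harm are 0.050, 0.144 and 0.287. Those favouring linagliptin fall to 0.011, 0.002 and 0.0005, so this case carries no risk of spurious benefit.

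**5. Smaller SD.** The plan's proviso asks for a residual SD below the difference. With SD 20, medications-only power is 0.916. The written model gives 0.887 to 0.940 at a 0.1% shift, and from 0.958 down to 0.494 at 0.3% to 0.5%.

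**6. Does the model isolate a glycaemia-independent effect?** In this simulation HbA1c has no causal effect on JNK-1; the correlation comes from shared causes. The effect independent of HbA1c is therefore -24, yet at a shift of 0.3% and ρ = 0.5 the model returns -16.8.

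**The case against.** The strongest reply concerns size. Every large figure above needs inputs the documents do not give. Entry requires HbA1c of 7.5% or below, so the shift may be small, and at 0.1% the distortion is minor. The prior sitagliptin data also suggest that much of the effect may bypass HbA1c: several inflammatory markers and NFκB binding fell after a single dose, before HbA1c could move. JNK-1 is not among those single-dose markers, however, and shared causes could still bias the coefficient. The point about size stands: the harm is possible but not demonstrated.

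A second reply concerns intent. The background argues for a direct anti-inflammatory action, so the investigators may have wanted an effect beyond glycaemia. No hypothesis or aim says so, and step 6 shows that this model would not reliably deliver it.

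Third, the reference to residual SD could hint that sizing had the adjusted model in mind. But the 24-point difference and the 24% SD both come from overall changes, and the unadjusted calculation reproduces the 20 per group.

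Finally, BMI is a weaker case, since the plan expects no change in either arm, and the single-dose point concerns a secondary endpoint in 24 patients. Both concessions are fair, and the conclusion does not depend on either.

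**Conclusion.** The concern holds: the analysis rule is wrong as written for the stated primary endpoint and must be fixed. Confidence is high that the model and the endpoint have different targets. This follows from the plan's own text: one model for everything, a covariate that treatment is said to move, and a primary contrast and sample size that describe the total difference from placebo.

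Confidence in the size is low. It depends on an assumed HbA1c shift, an assumed SD of HbA1c change and an assumed correlation, and ranges from negligible to halving the estimate (-24 to -12). The sign is also open, so the error could hide a real effect or inflate the chance of a false one. Even with zero correlation, where there is no bias, power is 0.67 to 0.76 instead of 0.79.

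**What to change.** In Data Analysis, remove change in BMI and change in HbA1c from the ANCOVA for the primary and all secondary endpoints. Keep treatment and pre-randomisation covariates only: baseline medications as already planned, with the baseline value of the endpoint as an option. Amend the matching sentence in the drop-out paragraph.

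If the adjusted model is of interest, report it for 12-week endpoints only, labelled exploratory and descriptive. State that it does not identify an effect independent of glycaemia, because causes shared by HbA1c change and the endpoint can bias it.

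The cost is one sentence changed in each of two paragraphs and one added, with no new patients, visits or measurements. The change should be made before unblinding. The downside is that the main result will not speak to glycaemia-independent effects.

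### The residual-SD condition attached to the 80% power claim is the unadjusted t-test limit; for the planned three-covariate ANCOVA with 17 completers per group the limit is about 23%, not just under 24%.

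*Combined protocol and SAP*

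**What the plan says.** All of this is in the DATA ANALYSIS section. Each endpoint is to be compared by "an analysis of covariance model, with baseline medications, change in BMI and change in HbA1c as covariates". The primary endpoint is the change in JNK-1 protein in mononuclear cells against placebo.

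The planning values come from an earlier sitagliptin trial: "a 24% fall (with SD of 24%) in JNK-1 following 12 weeks of treatment". For the control arm, "There was a 6% non-significant increase in JNK-1 protein in the placebo group in that study". The plan takes a difference of 24 points, alpha 0.05 and beta 0.2. It concludes that 20 per group with 15% drop-out is adequate, "provided the standard deviation of the residuals is not equal to or greater than the mean difference". The sample size table gives 17 per group in each of the three cells where the difference equals the SD (10/10, 15/15 and 20/20).

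The next paragraph, on the drop-out rate, takes up adjustment. It says "The analysis will adjust for only one baseline covariate: baseline medications" and names the changes in BMI and HbA1c as the other two covariates. It expects balance on one drug class ("The use of thiazolidinediones should be equally distributed among the two groups") and puts a figure on that adjustment alone: "adjustment for thiazolidinediones should decrease sample size by <5" per cent. It then says "we have estimated that our drop-out rate will be 15% of 20 patients", which is 3 per group.

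**The concern.** By referring to residuals, the plan states its power condition for the covariate-adjusted model. The number in the condition, however, is what an unadjusted comparison gives. Adjusting for covariates that differ between arms by chance makes the treatment estimate less precise at any given residual SD. A limit taken from the t-test is therefore too lenient for the ANCOVA.

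What is at stake is whether every residual SD that the condition admits delivers the stated beta of 0.2. The matter is not remote, because the only SD the plan cites is 24%, at the edge of the condition.

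**Working it through.** **Inputs from DATA ANALYSIS.** Difference d = 24 points; alpha 0.05; power 0.80; 20 per group less 3 drop-outs, so n = 17; three covariates.

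**Assumptions.** The test is two-sided. The documents do not say so, but a one-sided test needs about 13 per group when difference equals SD (normal approximation), and the table shows 17. Each covariate takes one model term. Covariates differ between arms by chance only; STUDY DESIGN describes randomisation into two groups without stratification.

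**Step 1: reproduce the plan's figure.** For a two-sample t-test, the noncentrality is d / [SD × √(2/n)] with 2n − 2 degrees of freedom.
- At SD 24: 24 / (24 × √(2/17)) = 2.915, with 32 df and critical value 2.037. Power is 80.7%.
- The smallest n giving 80% is 17, and 17 / 0.85 = 20. The plan's number reproduces.
- Solving for the SD that gives exactly 80% at n = 17 yields 24.2%. The plan's boundary of 24% is this limit.

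**Step 2: allow for lost degrees of freedom only.** Three covariates leave 34 − 2 − 3 = 29 df, critical value 2.045. At SD 24 power is 80.4% and the limit is 24.1%. On this count alone the plan's condition stands.

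**Step 3: add chance imbalance.** With q covariates unrelated to treatment, the variance of the adjusted treatment difference is multiplied by 1 + [q/(2n − 1 − q)] × F, where F follows an F distribution on q and 2n − 1 − q df.
- For q = 3 and n = 17 the mean factor is 1 + (3/30) × (30/28) = 31/28 = 1.107.
- At the mean factor and SD 24, the noncentrality is 2.915 / √1.107 = 2.771.

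Power averaged over the F distribution:

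| Residual SD | t-test | ANCOVA, lost df only | ANCOVA, chance imbalance |
|---|---|---|---|
| 22.8% | 84.5% | 84.3% | 80.5% |
| 23.0% | 83.9% | 83.6% | 79.9% |
| 23.5% | 82.3% | 82.1% | 78.2% |
| 23.9% | 81.0% | 80.8% | 76.8% |
| 23.99% | 80.7% | 80.5% | 76.5% |
| Limit for 80% | 24.2% | 24.1% | 22.96% |

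Simulation at SD 24 gave 76.7% with three normal covariates, and 76.1% with one of them replaced by a binary covariate at 20% prevalence.

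**Step 4: how the limit moves.**
- Number of terms at n = 17: one 23.8%, two 23.4%, three 22.96%, four 22.5%, five 22.1%.
- Completers per group with three terms, at SD 24: 18 give 79.2%, 19 give 81.6%, 20 give 83.8%.
- True difference of 30 points (24% fall, 6% rise), SD 24, n = 17, three terms: 91.7%.

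**Step 5: compare with the plan's allowance.** The average information lost is 1/31 = 3.2% for one term and 3/31 = 9.7% for three. The plan's figure of under 5% fits the single term to which it is attached. It does not cover all three covariates.

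**The case against.** The strongest reply is that nothing was miscalculated. The 20 per group follows from the plan's inputs, and counting lost degrees of freedom leaves the condition intact. Only the imbalance term breaks it, and a planning statement is an approximation. The gap also needs several things together: a residual SD between about 23% and 24%, a true difference close to 24 points (25.1 points restores 80% at SD 24), and at least two drop-outs per group. The prior SD came from 12 treated patients; under normality its 95% interval runs from about 17% to 41%, so separating 23% from 24% is finer than the data allow.

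Most of this stands, and it fixes the size of the point. It does not remove the point. With no stratification described, some imbalance is expected in the planned analysis, and the plan itself chose to state a numerical boundary for the residual SD. The gain from covariates that explain outcome variance is no answer either, because a condition on the residual SD already counts it.

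A reader might infer that the trial is underpowered, that 20 per group is wrong, or that a negative JNK-1 result could not be interpreted. The documents support none of these. The sample size reproduces, the planned difference is below the 30 points seen before, and a negative result would be read from its estimate and confidence interval.

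**Conclusion.** The power condition is wrong as written, by a small amount. With 17 completers per group and a 24-point difference, the planned ANCOVA reaches 80% power only up to a residual SD of about 23%. Between there and 24% the stated beta of 0.2 is missed by at most about 3.5 points.

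This rests on the assumptions listed in the working. More than one term for medications would lower the limit. So would a systematic difference between arms in HbA1c change, which is measured after randomisation on a drug that the protocol's rationale credits with better glycaemic control. For illustration only, an assumed treatment–covariate correlation of 0.3, with no chance term added, gives a limit of 23.0%. The point is minor.

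**What to change.** In the sample size paragraph of DATA ANALYSIS, replace the condition with wording such as: *provided the residual SD is about 23% or less (17 completers per group, three single-term covariates, chance imbalance only; lower if medications need more terms or if HbA1c change differs between arms)*. Equivalently, keep 24% and state that power there is about 76% to 77%.

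The change is to text only. Enrolment, endpoint and model stay as they are. The cost is a slightly less favourable power condition.
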